**Participant Time-Line**

Week	Procedure
-1	Screening to determine eligibility and Informed Consent
0	Baseline Assessment, and Randomization
1-13	Intervention Condition with Weekly Alcohol Use Assessments & Breathalyzer & Alcohol Urine Toxicology Screen
7	Cognitive Assessment
13	Complete Intervention Condition and Follow-up 1 Assessment
26	Complete Follow-up 2 Assessment

Blinding: This is possible because of our ability to have specialized staff for each purpose. Cognitive Remediation/ Individual Drug Counselors (IDCs) are required to be un-blinded in order to provide support for participants in their assigned conditions. They will be distinct from the psychometrician doing weekly and follow-up assessments. Blinded Roles: Staff responsible for the administration and scoring of participants' assessments after randomization will remain blinded to participant treatment condition. To prevent un-blinding, the following controls will occur: 1. The treatment condition (CRT+IDC) and the control condition (Game-Play Placebo+IDC) will be identified as "Cognitive Training A" and "Cognitive Training B"; 2. Participants will be reminded not to discuss details related to treatment with the psychometrician prior to the start or at the conclusion of their visit (a sign on the desk reminds the participant of this rule); 3. Research staff will be instructed not to discuss details of treatment related to either cognitive training arm during informed consent or at any other point throughout the study. The informed consent accurately describes this study as a comparison of two approaches to using challenging computer games to improve cognition. Every effort will be

made to avoid the implication that one condition is the experimental condition and the other is the control condition. 4. Accidental un-blinding of the psychometrician (e.g. through the un-intended viewing of treatment sessions) will be avoided. 5. Signs will be posted in appropriate areas reminding staff and participants not to discuss treatment details in open locations. 6. Mid-way and at the end of the trial, the psychometrician will be asked questions to evaluate the integrity of the blinding procedures employed throughout the trial. The psychometrician will complete a rating of degree of blindness (Definite CRT+IDC to Definite Game-Play Placebo+IDC) after each assessment. The primary outcome of Heavy Drinking Days and Days of Use is relatively immune to bias, particularly since it is informed by chart review and weekly Breathalyzer testing. All procedures are already in place and were successfully implemented in the R21.

### **Treatment Conditions**

Individual Drug Counseling (IDC): Once randomized to condition, all participants meet individually each week with their Individual Drug Counselor, who follows the manualized IDC treatment. All participants receive these procedures during the 13 weeks of active intervention. IDC has been summarized in a published manual for study therapists. It is based on the disease model of addiction. Clients are counseled regarding such fundamental concepts of AUD treatment as pointing out when a client is denying the extent and consequences of alcohol use, teaching clients to avoid “people, places and things,” and encouraging clients to make a personal inventory of qualities to change. It is practical and behavioral, with a focus on abstinence in the here and now. The manual describes sessions devoted to treatment engagement, early abstinence and maintenance of abstinence. IDC does not prevent clients from getting the treatment-as-usual they have been getting prior to enrollment. In addition to standard IDC, several adaptations have been made to IDC for this study. These include a) research staff will make phone calls to remind participants of their appointments and to coordinate with other clinicians to schedule appointments; b) weekly appointments will be scheduled over 13 weeks, with rescheduling and drop-in appointments allowed; c) abstinence is presented as desirable but to prevent the Abstinence Violation Effect (a slip becoming a full-relapse), relapse prevention and harm reduction will be emphasized; and d) participants are encouraged to participate in available AUD treatment groups at VACHS, whereas classic IDC more specifically refers to Twelve Step groups.

CRT and Game-Play Placebo: This study employs two computerized programs for cognitive enhancement. The CRT+IDC condition uses BrainHQ and the Game-Play Placebo uses a set of ordinary computer games. Participants will be asked to use their assigned program for one hour per session, up to five sessions per week, over three months (maximum of 65 sessions). A particular advantage of this training is that after participants are trained in how to log on to the training website and are familiar with the training programs, they may continue their training on site at the Learning Based Recovery Center (LBRC)’s “Cog Lab” or at another quiet location of their choice. If the participant prefers, it is also possible to use the program on their own device at home, use a computer available at their residence or a computer at a local library. The program allows participants to change locations as fits their schedule. Usage and progress tracking for both programs is completely web-based, allowing participants to move between computers as is convenient for them. Research staff carefully monitor usage and progress each week and use that information in phone call counseling sessions regardless of condition assignment.

Also, while we will encourage participants to complete 5 sessions per week of training, we will also let them know that we understand that not every participant will be able to maintain this schedule. We will let them know that if they feel they need to drop to a lower number of sessions per week that they should discuss it with their research counselor who will work out a schedule that is feasible in their overall life circumstances. There are also circumstances in which the participant may wish to practice more than 5 sessions in a week, particularly when they missed some practice days in a previous week. This is allowable but should be discussed with the participant’s research counselor. Participants may also choose to do their computer-based training even if they miss a weekly IDC appointment. The research counselor will contact the participant by phone to encourage continued participation and to learn about any alcohol or other substance use during the week. If a participant wishes to stop or minimize use of the training program, they will still be encouraged to continue their IDC sessions, and contact will be maintained by phone, if possible, even if the participant does not regularly come to IDC sessions. Potential reasons for discontinuing might include a change in work circumstances, a change in residence, health issues, family/personal issues, relapse or a lack of interest in program activities. However, the participant may want to meet their personal commitment to the basic scientific research of the study and will be encouraged to participate in follow-up assessments.

Brain HQ is a computerized cognitive remediation program consisting of a set of specific cognitive exercises and is commercially available on the internet. To disguise to which condition the participant is assigned, Posit Science created a special study log-in site so that a participant encounters the same initial screens when entering the system regardless of condition. This special study website was created for the DoD funded mTBI study (BRAVE) currently in progress, and Posit Science has agreed to allow us to use it for the this study. To use BrainHQ, a participant opens a standard web browser on a broadband connected computer and goes to the study website. The participant then logs into the website (using a study-provided screen name that contains no personally identifiable information). A game-like experience begins, where the participant is encouraged to earn points and in-game rewards to advance. To do so, the participant selects one of the cognitive exercises scheduled for the day, and performs that exercise for fifteen minutes. After each trial, the difficulty of the next trial is updated to ensure that within a session, the participant gets ~85% of trials correct. Summary screens including game metrics (points, levels) and exercise metrics (usage, progress) are shown to the participant at the end of each session. BrainHQ has multiple cognitive exercises. The scheduling mechanism ensures that the participant progresses through the exercises in a defined order, generally moving from simpler (early sensory processing) exercises to more complex (multimodal, cognitive control) exercises over the course of the three month experience. At any point in time, the participant only has access to a subset (typically six) of these exercises, four of which are performed per day. Each exercise has specific criteria for completion or plateaued performance, and after those criteria are met, the exercise is removed from the active set and the next exercise is added to the active set. This ensures ongoing novelty and engagement, while allowing for smooth progression through the complete set of exercises. The exercises include many of the auditory and visual tasks used in our R21 pilot study that address attention, working memory, processing speed, memory and learning, and executive function

Game-Play Placebo: The active control program is composed of 13 ordinary computer games. It is designed to 1) be a face-valid approach to cognitive remediation to maintain participant blind and match BrainHQ in any halo or expectation effect, 2) match BrainHQ in overall program use intensity, requirements for attention, delivered rewards, and overall engagement, and 3) provide a comparison group that matches BrainHQ with the exception of the specific scientific approach to cognitive remediation embodied by BrainHQ to allow the study results to be interpreted in light of that specific approach. The Game-Play Placebo is launched in the same manner as BrainHQ. The participant chooses from a number of ordinary computer games (e.g., hangman, boggle, word scramble, chess). The games are chosen for their face-validity in improving cognitive function. The number, availability, and time spent on each game is managed by the game controller to generally match the experience of progress through BrainHQ. Only games providing face-valid cognitive stimulation and that are rated E (for everyone) by the Entertainment Software Rating Board (ESRB) will be used. This is the same control condition currently in use in the DoD funded mTBI study (BRAVE).

### **Participant Compensation**

To encourage participation, small incentives are included in this study to compensate for time and inconvenience. Participants will receive \$50 for the interview and screening procedures, \$25 for the 7 week assessment, \$75 for 3 month follow-up, and \$75 for 6 month follow-up, for a total of \$225 for assessments. They will receive \$10.00 for each individual session of Individual Drug Counseling plus \$5.00 for the breathalyzer test during 13 weeks for a maximum total of \$195.00. They will also receive \$5 per hour for time spent doing cognitive training for a maximum total of \$325 for 65 hours of training. The maximum total compensation for full participation in all procedures over 26 weeks is \$745. Payment will be made according to current VA procedures. They may choose to have a check mailed to the address they provide or they may choose electronic fund transfer (EFT) if they provide required banking information or they may choose to receive gift certificates for use at the VCS canteen (retail store) or VCS cafeteria here at the VA

### **Concomitant Treatment and Staff Training**

Approach to Concomitant Treatment: The aim of this study is to determine efficacy in an outpatient setting, and there will be wide variability in how much participants utilize concomitant treatment-as-usual. Concomitant treatment will be tracked using our Treatment Utilization form to determine whether CRT+IDC increases participation in concomitant treatment and if such an increase mediates its effect on AUD outcomes. All participants will have access to a VA primary treating clinician. Primary clinicians will coordinate the participant's access to other available treatments including a prescribing physician, restricted settings (inpatient, day hospital and detoxification), residential assistance (supervised housing, group homes, rent

assistance), outpatient substance abuse treatment, and vocational rehabilitation. Participants are encouraged to remain engaged in outpatient services and to do so throughout the study. Their study condition is meant to be an augmentation to their usual treatment at VACHS. Part of the consent process includes permission for research staff to speak with their clinician and to convey clinically relevant information at the discretion of the PI. Moreover, all participants will have at least monthly notes recorded in their electronic medical record relevant to clinically related events that may occur during research activities. This is carefully explained in the consent form and is for the medical welfare of the participant. These procedures are to ensure that participants experience the study intervention as an augmentation to their on-going AUD treatment.

Therapist Training to Conduct Individual Drug Counseling: Training will be overseen by [name] and will employ multiple modalities: review of the therapy manual, role plays, and group meetings to discuss problematic aspects of the therapy. Digital recordings of IDC delivered as part of [name] RO1 are available from the NIAAA website. Hiring counselors who have an AUD treatment background is important because when experienced counselors deliver IDC, it is readily learned and delivered with fidelity. In the main clinical trial, IDC was the intervention rated as being delivered with the highest fidelity to the manual.

Therapist Supervision of IDC: The therapist will be supervised intensively by [name] until the therapist understands IDC and delivers it effectively, as verified by review of therapy videotapes and therapy notes. [name] will not be one of the independent raters of the videotapes for fidelity purposes and thus, will be able to review the videotapes in supervision without compromising the ratings' impartiality. After the initial period, supervision will be phased back to weekly, with as-needed consultation.

Assessment Training. The psychometrician is independent of the research counselors and is kept blind to condition. Our assessors have already been trained through our previous research. [name] monitors the procedures and carefully reviews assessment data weekly for any inconsistencies that may suggest errors in scoring or data entry. If new staff is added during the course of the proposed study, [name] takes responsibility for training them in these procedures by having them observe assessments, perform assessments under his supervision and by determining inter-rater agreement. In the proposed study, the only clinical assessments are MINI diagnosis at baseline, the Time Line Follow-back Alcohol Use Calendar, and the ASI.

## **Data Management, Sample Size Calculation, and Analysis Plan**

Data management will follow procedures established in previous studies. Our research team will use Teleforms® software to create, clean, and enter quantitative data. Forms are created with barcodes that are scanned using Teleforms' object character recognition software. Data is extracted and automatically inputted to an SPSS database. Filters flag data that needs to be re-checked by a person such as unclear characters, out-of-range variables and logical inconsistencies. The research assistant will scan files monthly so that errors can be readily corrected and consequential differences between treatment types (e.g., different levels of attrition) can be monitored closely. SPSS (vers. 21) will be used as the primary analysis software. Baseline characteristics will be tested for any significant differences between randomized conditions using parametric and non-parametric procedures as required by the nature of the data. Data reduction is a major issue in a relatively small N, large-number-of-variables study. We have chosen a primary outcome measure (Heavy Drinking Days and Days of Use in the first 90 days) to reduce Type I error. Heavy Drinking Days and Days of Use will be determined by Time-Line Follow-back calendar and Breathalyzer results. If a participant cannot provide more exact information about days of use for that week, then we will assume continuous use.

Neuropsychological data will be indexed into established domain scores (attention, working memory, memory and learning, executive function, processing speed) and a composite index score. The design is intent-to-treat. Distributions of continuous data will be tested for normality and transformed when necessary. Randomized conditions will be tested for potential differences on baseline values. We believe that our stratified randomization will make it unlikely that significant differences will be found; however, any significant differences will be used as covariates in between-group comparisons.

Sample size: We plan to screen approximately 150 Veterans and recruit 110 Veterans (after telephone screen) with a current and primary DSM-V AUD who are within the first 30 days of recovery and expect that 90 will be eligible for randomization after baseline testing. We expect better than a 90% retention rate at the 3 month time point, and thus expect to have more than 80 individuals for the primary analysis. Assuming equal loss-to-follow-up in each of the two treatment arms, we will have at least 40 individuals per group. Using data

from our pilot study and the study done by Bowen et al., we estimate mean Days of Alcohol Use in the Placebo + IDC arm to be 4 and the number of Heavy Drinking Days to be 3 at 90 days. Using PASS 12 (Kaysville, Utah) Poisson regression procedure, and assuming an over-dispersion parameter of 2 for days of use and 4 for heavy drinking days, we will be able to detect a 37% reduction in days of use and a 55% reduction in days of heavy drinking with 80% power and a type I error rate of 5% for each outcome in the CRT+IDC arm compared to the Game-Play Placebo + IDC arm. Stratification on neurocognitive functioning was not factored into the sample size calculations. In most situations, stratification will increase precision, and thus we will have a conservative estimate of the detectable effects. Given that we expect to lose another 5-10% of individuals to follow-up, we will have less power to detect the same effect size at 6 month time point.

Analysis Plan: We will use a Poisson regression model accounting for over-dispersion to compare the CRT+IDC arm to the Game-Play Placebo+IDC arm on the primary outcomes: Days of Use and Days of Heavy Drinking at 90 days (Ho1). We will use the same model to compare the CRT+IDC arm to the Game-Play Placebo+IDC for the 6 month time point, a secondary endpoint (Ho2). We will conduct sensitivity analysis using a negative binomial model and assess any differences in the results compared to the Poisson model with over-dispersion. To evaluate neurocognitive functioning (global index; index of working memory; index of executive function, etc..), we will use generalized estimating equations and/or linear mixed models (if the data appear normally distributed) to account for the correlation between time points (baseline, 3 months, 6 months) for a given individual. We will test for a significant treatment arm by time interaction to determine whether the combination of CRT+IDC is more effective than Game-Play Placebo+IDC in improving neurocognitive outcomes (Ho3, Ho4). We use contrast statements to explore the individual time point effects. In all models, we will adjust for neurocognitive functioning (the stratification variable). We will use the Benjamini-Hochberg procedure to control the false discovery rate for all secondary outcomes keeping the overall level of significance at 0.05. However, given the limited sample size in this study, we do not expect to reach statistical significance unless there are large effects, especially for the secondary outcomes, and thus plan to use these results as hypothesis generating for a larger confirmatory study.

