*Ho1: CRT+IDC will be more effective than Game-Play Placebo+IDC in reducing heavy drinking days and decreasing days of use as measured by Breathalyzer and Timeline Follow-back Method (TLFB) during the 90 days of active intervention.*

**Secondary Aim #1:** To determine if CRT+IDC is more effective than Game-Play Placebo+ IDC in sustaining decreased alcohol use in older Veterans at the end of 6 months (3 months after the active intervention period).

*Ho2: CRT+IDC will be more effective than Game-Play Placebo+IDC in reducing heavy drinking days and decreasing days of use as measured by Breathalyzer and Timeline Follow-back Method (TLFB) for the 30 days preceding 6 month follow-up.*

**Secondary Aim #2:** To determine if the combination of CRT and IDC is more effective than game play placebo and IDC in improving neurocognitive functioning.

*Ho3: Veterans receiving CRT+IDC will show greater improvement than Veterans receiving Game-Play Placebo+IDC at 3 month follow-up on a global index of neurocognitive function, and on an index of working memory and an index of executive function.*

*Ho4: Differential improvements in neurocognitive function will be sustained at 6 month follow-up*

**4. Background:** Alcohol Use Disorders (AUDs) have a significant public health impact, cost billions of dollars in the US each year for treatment and lost productivity, and are highly prevalent in Veterans. Estimated point prevalence is 5.5% in returning Veterans, higher than the 3.8% civilian estimate. Lifetime prevalence for Vietnam Era Veterans was much higher when examined approximately 15 years after the end of the war, at almost 40% in men as compared to male civilians at 30%. Psychosocial behavioral interventions have some efficacy, but as revealed in a large VA cooperative multi-site study of a pharmacological augmentation (naltrexone), a high proportion in all arms of the study relapsed within one year. A recently published study of the relative efficacy of mindfulness-based relapse prevention in a civilian sample reported that 19% in the treatment as usual condition had returned to heavy drinking within 3 months. AUD is a major cause of suffering and functional disability for Veterans and a common co-morbidity with other physical and mental disorders. There is, therefore, a critical need to explore ways to improve treatment for AUDs in Veterans.

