Exclusion criteria: Lifetime diagnosis of a psychotic disorder, not induced by drug use; current prescribed treatment of opioids or benzodiazepines, which may affect new learning; involvement in a legal case that may lead to incarceration during study period; residential plans that would interfere with participation; medical illness that may significantly compromise cognition (e.g. Parkinson's, Alzheimer's, Huntington's Chorea, Moderate or greater TBI); an uncorrected sensory impairment (hearing or sight) that would seriously interfere with cognitive training; pre-morbid IQ estimate below 70; unstable housing or lack of commitment to staying within a geographic area that would make follow-up possible); unwillingness to provide contact information of someone who can help us contact the participant in the event that we are unable to maintain contact directly. They must be competent to give written informed consent and HIPAA authorization.

**Measures:** Primary outcome measures are Heavy Drinking Days and Days of Use for the 90 days of active intervention as measured by Time-Line Follow-back (TLFB) Alcohol Use Assessments. This assessment asks for days of use and how many drinks and what types of drinks were consumed at each occasion during the preceding week. Other drug use is also recorded. TFLB assessment is done weekly along with an alcohol urine toxicology test and a Breathalyzer test. If more than one week has passed since the last TFLB assessment, the TLFB procedure is used to review the entire lapsed period. For example, if it has been 14 days since the last TLFB, then going backwards, the interviewer would ask about alcohol use for those 14 days. Breathalyzer testing and an alcohol urine toxicology test is always performed first, followed by the TFLB. This sequence encourages disclosure even though Breathalyzer results only reflect alcohol use during the past day. The alcohol urine toxicology test reflects a window of up to 80 hours of prior use. A positive Breathalyzer test and an alcohol urine toxicology test is regarded as definitive evidence of alcohol use and has precedence over self-report when the person denies use. However a negative Breathalyzer test or a negative alcohol urine

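### A week with inexact use information is scored as 7 use days against a planned 90-day mean of 4; the rule may fire unequally by arm, leaves heavy days undefined, and no sensitivity analysis tests it

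*Combined protocol and SAP*

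**What the plan says.** The rule is in the section on data management, sample size and analysis, directly after the statement that both primary outcomes come from the Timeline Follow-back (TLFB) calendar and Breathalyzer: "If a participant cannot provide more exact information about days of use for that week, then we will assume continuous use". It is part of the primary outcome definition, not a sensitivity analysis.

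The sample size paragraph of that section gives the scale: "we estimate mean Days of Alcohol Use in the Placebo + IDC arm to be 4". Its corresponding figure for heavy days is 3.

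Under Measures in section 6, the TLFB is weekly, but after a missed visit the recall period lengthens: "If more than one week has passed since the last TFLB assessment, the TLFB procedure is used to review the entire lapsed period". The same text says that a negative breath or urine test does not count as abstinence when the participant reports use, so tests cannot reduce imputed days.

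Ho3 in section 3 expects CRT to outperform the placebo "on a global index of neurocognitive function, and on an index of working memory and an index of executive function". The Background section reports that verbal learning recovered under CRT in pilot participants with alcohol use disorder.

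The Analysis Plan names one sensitivity analysis for the primary outcomes, a negative binomial model. Nothing provides for counting imputed weeks, comparing them by arm, or scoring them another way.

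**The concern.** The rule depends on whether a participant can account for a week, and the intervention is meant to improve cognition. If CRT participants give more exact reports, fewer of their weeks are scored as 7, and their Days of Use falls with no change in drinking. A cognitive effect would then feed into the primary drinking comparison through the scoring. If the rule fires equally in both arms, it adds large jumps to a low count, which raises dispersion and costs power.

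There is a separate gap for the other primary outcome. A heavy drinking day is defined by number of drinks, but the rule assigns no quantity to an imputed day.

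The negative binomial model cannot reveal either problem, because it is fitted to the same imputed counts.

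**Working it through.** **Inputs from the plan.** 40 analysed per arm; control mean 4 for Days of Use and 3 for Heavy Drinking Days; dispersion 2 and 4 respectively; power 80% at a 5% error rate per outcome. The detectable effects are given as: "we will be able to detect a 37% reduction in days of use and a 55% reduction in days of heavy drinking".

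**1. The plan's own figures.** I took the procedure to be the Signorini formula for Poisson regression with a binary covariate, two-sided 5%:

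N = φ(1.96·√4 + 0.842·√(2 + 2/RR))² / (μ·(ln RR)²)

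- Days of Use (φ = 2, μ = 4, RR = 0.63): N = 79.7.
- Heavy Drinking Days (φ = 4, μ = 3, RR = 0.45): N = 76.7.

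Both agree with the planned total of 80, so the stated detectable effects are reproduced.

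**2. Weight of one imputed week.** 7/4 = 1.75 times the planned mean. The 37% target is 0.37 × 4 = 1.48 days per person. With the control mean held at 4 and no true effect, the between-arm difference in imputed weeks that would produce all of it is:

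| Days added per week | Weeks per person | Weeks per 40 | Share of person-weeks (90/7 = 12.86 each) |
|---|---|---|---|
| 6 | 1.48/6 = 0.247 | 9.9 | 1.9% |
| 3 | 1.48/3 = 0.493 | 19.7 | 3.8% |

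**3. Spurious reduction under unequal firing.** Assumptions: negative binomial counts with mean 4 and variance 8; no drinking effect; a share p of drinkers has one imputed week that truly held 2 days. The variance gives shape k = 4, so P(0) = 0.5⁴ = 0.0625 and P(1) = 4 × 0.5⁵ = 0.125. The rule adds 5 days, or 6 for someone with only one use day, so the mean rises by p(5 × 0.9375 + 0.125) = 4.8125p. False-positive rates come from simulation with a quasi-Poisson Wald test.

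| Firing, control vs CRT | Means | Ratio | Spurious reduction | False positives |
|---|---|---|---|---|
| none | 4.00 vs 4.00 | 1.00 | 0% | about 5% |
| 5% vs 2.5% | 4.24 vs 4.12 | 0.97 | 3% | about 5.5% |
| 10% vs 5% | 4.48 vs 4.24 | 0.95 | 5% | about 6% |
| 20% vs 15% | 4.96 vs 4.72 | 0.95 | 5% | about 6% |
| 20% vs 10% | 4.96 vs 4.48 | 0.90 | 10% | about 10% |
| 30% vs 10% | 5.44 vs 4.48 | 0.82 | 18% | about 23% |

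If each imputed week adds only 2 days, 20% vs 10% gives 4 + 0.2 × 0.9375 × 2 = 4.375 against 4.1875: a 4% reduction with 5.9% false positives. If firing is instead a share of drinking weeks, where most hold one true day, 10% vs 5% gives a ratio of 0.84 and 16% false positives. The result depends heavily on inputs the plan does not supply.

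**4. Equal firing.** With a true ratio of 0.63 and 10%, 20% or 30% of drinkers affected in both arms, power falls from 73% to about 61%, 55% and 51%. The 73% start reflects the Wald test against the formula's 80%; it is not caused by the rule. With no true effect and 5% or 10% of drinking weeks imputed in both arms, rejection stays near 5%, but dispersion rises from 2 to about 3.3 or 4.3.

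**5. Heavy Drinking Days.** With no quantity assigned, one imputed week can contribute 0 to 7 days to an outcome with planned mean 3. This needs no firing-rate assumption.

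**The case against.** Several points on the other side stand.

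- **Poor memory is not named as the trigger.** A reader might infer that it is. The text says only that the participant cannot give more exact information. Denial after a positive test, evasiveness or limited contact would also fit, and a rough count of days might already be exact enough to avoid the rule.
- **The link to CRT is indirect.** The indices singled out in Ho3 are global, working memory and executive function, not learning and memory. The pilot's verbal learning result concerns word lists, not recall of last week's drinking. Cognitive gains build over time, while the outcome counts all 90 days.
- **Pilot experience.** Cognition improved under CRT with no difference in substance use. That is mild contrary evidence: there were 24 per arm, and the plan does not say the pilot used this rule.
- **Safeguards.** Recall normally covers one week, breath and urine tests come first, the assessor is blinded, assessment data are reviewed weekly and rater drift is checked. These should make vague weeks less common. They do not equalise recall between arms or define the heavy-day score.
- **The ceiling is easily overstated.** A reader might take the rule to add 7 days, or 14 after a two-week gap. If some use is already known, the addition is at most 6 in a week, and a two-week gap cannot add 14.
- **Dilution of the ratio depends on the model.** Firing per drinker moves a true 0.63 to 0.66–0.70; firing on 5–10% of drinking weeks leaves it at 0.64–0.65. The power loss appears either way.

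A midpoint score is not a clean replacement. If a participant can only endorse 1 to 7 days, the midpoint is 4; with a true 2 days and 30% vs 10% firing, a 9% spurious reduction and about 9.4% false positives remain.

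**Conclusion.** The concern holds as a conditional one. The plan builds into its primary outcome a rule under which a single week can exceed the planned 90-day mean. The rule may fire less often in the arm expected to gain cognitively, and no planned analysis would show it.

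The size is unknown. Under the per-drinker assumptions above, it runs from negligible (about 3% spurious reduction, 5.5% false positives) to serious (about 18%, 23%). The documents do not support saying that a CRT benefit would be an artefact, or that the rule must be dropped from the primary analysis. They do support saying that, as planned, a positive result could not be separated from unequal scoring. The missing heavy-day score is a definite gap at any firing rate.

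**What to change.** 1. For any week with inexact use information, have the blinded TLFB interviewer record the fewest and the most use days the participant can endorse, and the same for heavy drinking days.
2. State how many heavy drinking days an imputed week contributes.
3. Flag each imputed week and report the number by arm.
4. Repeat the primary analysis of both outcomes with those weeks scored at the minimum, midpoint and maximum. Describe a drinking benefit as robust only if it does not depend on the continuous-use score.

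The continuous-use rule may remain the primary score. The cost is a minimum and maximum entry for each outcome on the weekly form, a few lines of derivation text and a little more analysis.
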